## **11. MEASUREMENT OF EFFECT**

### **11.1 Development of symptomatic disease**

In this study, the final endpoint is development of symptomatic MM that requires therapy. This is defined as one of the following criteria (CRAB\* and Myeloma defining events< MDE):

- Increased calcium levels (corrected serum calcium  $>0.25$  mmol/dL above the upper limit of normal or  $>.275$  mmol/dL);
- Renal insufficiency (attributable to myeloma);
- Anemia (Hgb 2g/dL below the lower limit of normal or  $<10$ g/dL);
- Bone lesions (lytic lesions or generalized osteoporosis with compression fractures)
- Or any MYELOMA DEFINING EVENTS (MDE) as follows:
  - Clonal bone marrow plasma cell percentage\* $> 60\%$ 
  - An abnormal FLC-ratio  $\geq 100$  (involved kappa) or  $\leq 0.01$  (involved lambda)
  - 2 or more focal lesions on MRI or PET-CT studies

\* Participants with CRAB criteria that are attributable to conditions other than the disease under study may be eligible

#### **For measurement of response:**

In this study, patients must have measurable disease. The disease response will be assessed using criteria based on the International Working Group Uniform Response Criteria in Section 11.2.4. If the only measurable parameter is serum immunoglobulins free light chain (FLC), the participant will be followed by FreeLite™ Disease Response Criteria provided in Section 11.2.5.

Disease response by the Modified EBMT Response Criteria in Section 11.2.6.2 will also be collected on participants as a secondary measure.

**The same method of assessment and technique should be used for disease measurement at baseline and during follow-up. Disease response should be confirmed by two consecutive**

CONFIDENTIAL

This document is confidential. Do not disclose or use except as authorized.

**assessments.**

## 11.2 Antitumor Effect

### 11.2.1 Disease Parameters

**Measurable disease:** Measurable disease is disease that can be measured either by serum or urinary evaluation of the monoclonal component or by serum assay of FLC and is defined by at least one of the following three measurements:

- Serum M-protein  $\geq 0.5$  g/dl
- Urine M-protein  $\geq 200$  mg/24 h
- Serum FLC assay: Involved FLC level  $\geq 10$  mg/dl ( $\geq 100$  mg/l) provided serum FLC ratio is abnormal.

If a patient has measurable disease, but not by IMWG standards listed above, the patient may be eligible after discussion with the Overall Principal Investigator.

### 11.2.2 Methods for Evaluation of Measurable Disease

All baseline evaluations should be performed on Cycle 1, Day 1 of initial therapy. Response will be assessed by M-protein quantification, protein electrophoresis and immunofixation from serum and a 24-hour urine collection. A serum sample for FreeLite™ testing will be obtained. In addition, bone marrow aspiration and biopsy, as well as skeletal survey will be performed to determine overall response or confirm response.

**The same method of assessment and technique should be used for disease measurement at baseline and during follow-up.**

### 11.2.3 Response Criteria

A confirmation measurement for disease response assessments is required in this protocol.

### 11.2.4 International Myeloma Working Group Response Criteria

Response criteria for all categories and subcategories of response except CR are applicable

CONFIDENTIAL

This document is confidential. Do not disclose or use except as authorized.

only to patients who have ‘measurable’ disease, as defined in Section 11.2 All response categories require two consecutive assessments made at any time before the institution of any new therapy; all categories also require no known evidence of progressive or new bone lesions if radiographic studies were performed. Radiographic studies are not required to satisfy these response requirements.

**Stringent CR:** CR as defined below plus normal free light chain ratio and absence of clonal cells in bone marrow\* by immunohistochemistry or immunofluorescence.\*\*

\*Confirmation with repeat bone marrow biopsy is not needed.

\*\*Presence/absence of clonal cells is based upon the  $k/\lambda$  ratio. An abnormal  $k/\lambda$  ratio by immunohistochemistry and/or immunofluorescence requires a minimum of 100 plasma cells for analysis. An abnormal ratio reflecting presence of an abnormal clone is  $k/\lambda$  of  $> 4:1$  or  $< 1:2$ .

**CR:** Negative immunofixation on the serum and urine and disappearance of any soft tissue plasmacytomas and  $\leq 5\%$  plasma cells in bone marrow.

\*Confirmation with repeat bone marrow biopsy is not needed.

**VGPR:** Serum and urine M-protein detectable by immunofixation but not on electrophoresis or 90% or greater reduction in serum M-protein plus urine M-protein level  $< 100\text{mg}$  per 24 hours.

**PR:**  $\geq 50\%$  reduction of serum M-protein and reduction in 24-h urinary M-protein by  $> 90\%$  or to  $< 200\text{mg}$  per 24 hours. If the serum and urine M-protein are unmeasurable, a  $\geq 50\%$  decrease in the difference between involved and uninvolved free light chain levels is required in place of the M-protein criteria (definition of measurable disease in Section 10.2.3). If serum and urine M-protein are unmeasurable, and serum free light assay is also unmeasurable,  $\geq 50\%$  reduction in plasma cells is required in place of M-protein, provided baseline bone marrow plasma cell percentage was  $\geq 30\%$ . In addition to the above listed criteria, if present at baseline, a  $> 50\%$  reduction in the size of soft tissue plasmacytomas is also required.

**SD:** Not meeting criteria for CR, VGPR, PR or progressive disease. This is not recommended as an indicator of response; stability of disease is best described by providing the time to progression estimates.

**PD:**  $> 25\%$  increase of serum M-protein (which must also be an absolute increase of  $\geq 0.5\text{ g/dL}$ ) and/or urine M-protein (which must also be an absolute increase of  $\geq 200\text{ mg/24hr}$ ). If serum and urine M-protein are unmeasurable, there must be an absolute increase of  $\geq 10\text{ mg/dL}$  between involved and uninvolved FLC levels. PD is also measured by an absolute increase in bone marrow plasma cells  $\geq 10\%$ . In addition to the above listed criteria, progression may also be measured by a definite development of new bone lesions or soft tissue plasmacytomas or definite increase in the size of existing bone lesions or soft tissue plasmacytomas or development of hypercalcemia (corrected serum calcium  $\geq 11.5\text{ mg/dL}$  or  $2.65\text{ mmol/L}$ ) that can be attributed solely to the plasma cell proliferative disorder.

CONFIDENTIAL

This document is confidential. Do not disclose or use except as authorized.

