## 2.7 Elotuzumab

Elotuzumab (HuLuc63/BMS-901608) is a humanized monoclonal IgG1 antibody product directed to human SLAMF7 (CD2 subset-1, also known as CRACC), a cell surface glycoprotein with homology to the CD2 family of cell surface proteins. Originally, SLAMF7 was identified as a natural killer cell (NK) marker and was shown to be expressed in a subset of circulating leukocytes. Blood analysis confirmed expression of SLAMF7 on the cell surface of NK, NK-like T-cells (NKT), activated monocytes, CD8 positive T cells and on tissue plasma cells. High SLAMF7 expression was seen in plasma cells obtained from normal healthy donors and from patients with MGUS, SMM, and active MM. More than 90% of MM bone marrow samples, irrespective of cytogenetic abnormalities, express SLAMF7.. In addition SLAMF7 expression is maintained in MM subjects after relapse from therapy. A paired analysis of a subset of subjects with MM showed that SLAMF7 gene expression is detectable in subjects both at diagnosis and at relapse.

In agreement with the gene chip data, flow cytometry analysis demonstrated that CD138+ plasma cells from MM bone marrow stained strongly positive for elotuzumab binding. In addition, immunohistochemistry (IHC) using anti SLAMF7 antibodies showed strong staining of MM cells in 9/9 plasmacytoma tissue samples and in 20/20 myeloma bone marrow cores tested.

The proposed mechanism of action of elotuzumab involves natural killer (NK) cell mediated antibody dependent cell-mediated cytotoxicity (ADCC). Elotuzumab monotherapy can kill MM cell lines and primary myeloma cells in vitro in the presence of peripheral blood mononuclear cells (PBMCs) or purified NK cells. In addition, elotuzumab exhibits significant in vivo monotherapy anti-tumor activity against human myeloma xenograft models grown in severe combined immunodeficient (SCID) mice. This in vivo anti-tumor activity of elotuzumab appears to be largely dependent on the presence of active NK cells. Experiments using an in vivo mouse xenograft model suggest that maximal antitumor activity is reached at elotuzumab serum levels of 70 to 430 mcg/mL.

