#### 2.9.5.4 Clinical Pharmacokinetics

Blood samples were collected for estimation of serum elotuzumab concentrations following single and multiple dose administration in Studies 1701, 1702, and 1703. Preliminary pharmacokinetic (PK) analysis results limited to  $C_{min}$  and  $C_{max}$  have been reported for all 3 of these studies.

Following single dose administration (Study 1701) of escalating doses of elotuzumab alone,  $C_{max}$  increased with increasing dose over the dose range of 0.5 to 20 mg/kg. Following multiple dose administration of escalating doses of elotuzumab on Days 1 and 11 of a 21-day cycle in combination with bortezomib (Study 1702), the observed steady-state  $C_{min}$  values consistently remained above 70  $\mu$ g/mL, the minimum maximally efficacious trough concentration, following administration of the 10 mg/kg dose (296 to 698  $\mu$ g/mL) and the 20 mg/kg dose (572 to 1092  $\mu$ g/mL). Following administration of elotuzumab every 7 days for the first 2 cycles, and every 14 days for all subsequent cycles in combination with lenalidomide and dexamethasone (Study 1703), the steady state  $C_{min}$  concentrations associated with the 10 mg/kg dose ranged from 163 to 301  $\mu$ g/mL, which was above the minimum maximally efficacious trough concentration.

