#### 5.3.1 Elotuzumab

Elotuzumab will be administered intravenously at a dose of 10 mg/kg on Days 1, 8, 15 and 22 for the first 2 cycles (a cycle =28 days). During cycles 3 through 8, elotuzumab will be given on days 1 and 15. Elotuzumab will be administered intravenously at a dose of 20 mg/kg only on Day 1 for cycles 9-24. The patient should be observed for 60 minutes after the infusion is complete for cycle 1 and should be observed for 30 minutes after the infusion for subsequent cycles. All patients should have their vital signs checked before and after elotuzumab infusion or per institutional standard. If an infusion reaction occurs, reference section 6.4.2 for guidelines on additional vital monitoring.

Cycle 1 and Cycle 2 treatment may be administered +/- 3 days. For subsequent cycles +/- 7 days is allowed.

CONFIDENTIAL

This document is confidential. Do not disclose or use except as authorized.

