### 8.1 Elotuzumab

#### 8.1.1 Description

Elotuzumab (BMS- 901608; formerly known as HuLuc63) is a humanized recombinant monoclonal IgG1 antibody product directed to human SLAMF7 (CD2-subset-1, also known as CRACC), a cell surface glycoprotein that is highly expressed in MM cells.

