### 11.2.6 Criteria for Molecular CR and Minimal Residual Disease (MRD) measurement

We will measure MRD in patients who achieve CR to determine the number of patients who are MRD negative vs MRD positive.

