#### 11.2.6.2 Modified EBMT Response Criteria

Response	Criteria for Response a
Complete response (CR)	Requires all of the following:  Disappearance of the original monoclonal protein from the blood and urine on at least two determinations for a minimum of six weeks by immunofixation studies.  <5% plasma cells in the bone marrow on at least two determinations for a minimum of six weeks. b  No increase in the size or number of lytic bone lesions (development of a compression fracture does not exclude response). c  Disappearance of soft tissue plasmacytomas for at least six weeks.
Near Complete Response (nCR)	Requires the following:  Same as CR, but immunofixation studies continue to show presence of the monoclonal protein
Very Good Partial Response (VGPR)	Requires the following: $\geq 90\%$ reduction in serum M-protein plus urine M-protein level <100mg per 24 hours on at least two determinations for a minimum of six weeks.

CONFIDENTIAL

This document is confidential. Do not disclose or use except as authorized.

Partial response (PR)	
PR includes participants in whom some, but not all, criteria for CR are fulfilled providing the remaining criteria satisfy the requirements for PR. Required all of the following:
 
≥50% reduction in the level of serum monoclonal protein for at least two determinations six weeks apart.
 
If present, reduction in 24-hour urinary light chain excretion by either ≥90% or to <200 mg for at least two determinations six weeks apart.
 
≥50% reduction in the size of soft tissue plasmacytomas (by clinical or radiographic examination) for at least six weeks.
 
No increase in size or number of lytic bone lesions (development of compression fracture does not exclude response).c

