Relapse from CR	
Required at least one of the following:
 
Reappearance of serum or urinary paraprotein on immunofixation or routine electrophoresis confirmed by at least one follow-up and excluding oligoclonal immune reconstitution.
 
<math>\geq 5\%</math> plasma cells in the bone marrow aspirate or biopsy.
 
Development of new lytic bone lesions or soft tissue plasmacytomas or definite increase in the size of residual bone lesions (not including compression fracture).
 
Development of hypercalcemia (corrected serum calcium <math>>11.5</math> mg/dL or 2.8 mmol/L not attributable to any other cause).e

-----------------	--

- a Based on the criteria reported by Blade *et al.*, 1998.
- b Per Blade *et al.*, 1998, if absence of the monoclonal protein is sustained for 6 weeks it is not necessary to repeat the bone marrow except in participants with nonsecretory myeloma where the marrow examination must be repeated after an interval of at least 6 weeks to confirm CR.
- c Per Blade *et al.*, 1998, skeletal X-Rays are not required for the definition of response, but if performed there must be no evidence of progression of bone disease (no increase in size or number of lytic bone lesions).
- d It is suggested that the reference point for calculating any increase should be the lowest value of the preceding confirmed response (MR, PR or CR) or the baseline value if there is no previous confirmed response.
- e Other clinical data may be requested by the IRC, as necessary, to assess the cause of the hypercalcemia.

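### The main CR definition requires negative immunofixation without excepting the monoclonal IgG1 study drug, so CR, and MRD where it is tied to CR, can be under-counted by an unknown amount

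*Combined protocol and SAP*

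**What the plan says.** **Main CR rule.** Section 11.2.4 (IMWG criteria, the main response criteria) requires "Negative immunofixation on the serum and urine and disappearance of any soft tissue plasmacytomas", with no more than 5% marrow plasma cells. Every response category needs two consecutive assessments. The text gives no rule for a band that comes from treatment.

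**Secondary CR rule.** Section 11.1 has response collected by the modified EBMT criteria as well. There (11.2.6.2) CR is "Disappearance of the original monoclonal protein from the blood and urine" by immunofixation, which refers to the patient's own protein.

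**The drug.** Section 8.1.1 describes elotuzumab as a "humanized recombinant monoclonal IgG1 antibody product directed to human SLAMF7". Section 5.3.1 states: "Elotuzumab will be administered intravenously at a dose of 10 mg/kg on Days 1, 8, 15 and 22 for the first 2 cycles", then Days 1 and 15 in cycles 3-8, then 20 mg/kg on Day 1 only in cycles 9-24. Section 2.9.5.4 says that in Study 1703 (weekly for two cycles, then every 14 days, with lenalidomide and dexamethasone) the steady-state trough "concentrations associated with the 10 mg/kg dose ranged from 163 to 301" µg/mL.

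**Timing.** The study calendar (Section 10) has serum and urine immunofixation on Day 1 of every cycle, and assessments come before that day's study medication.

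**MRD.** Section 11.2.6: "We will measure MRD in patients who achieve CR to determine the number of patients who are MRD negative vs MRD positive". Section 13.1.2 reports the CR and MRD proportions with 90% exact intervals.

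**The concern.** From the second cycle on, an immunofixation gel may show the patient's residual M-protein, the drug, or both. The EBMT wording allows a drug band to be set aside. The main wording, read literally, does not. The same gel from the same patient could then be CR under the secondary criteria and something less under the main ones.

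Any resulting error runs in one direction: true CRs can be recorded as non-CR, never the reverse. It depends on drug level and band position rather than on disease, and no confidence interval reflects it. Where the MRD test is ordered because CR has been reached, a masked CR can also lose its MRD result. Nothing in Sections 9 to 11 or 13 mentions antibody interference or says how to judge a new or faint IgG band.

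**Working it through.** **1. The plan's own figures.** With n = 39, the widest exact (Clopper-Pearson) 90% interval over all possible counts is 28.1%, at 20 of 39; Section 13.1.2 says 28%. For the primary rule, P(X ≥ 24 | 39, 0.5) = 0.0998 (stated 0.10) and P(X ≥ 24 | 39, 0.7) = 0.906 (stated above 0.9). Both reproduce. The documents give no CR rate, MRD rate or immunofixation limit, so there is no stated figure to check on the point itself.

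**2. Drug level in M-protein units.** 1 g/dL = 10,000 µg/mL, so 163-301 µg/mL = 0.0163-0.0301 g/dL.

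**3. Trough against the detection limit.** The limit is an assumption. Ratio = trough ÷ limit.

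| Assumed limit (µg/mL) | 163 ÷ limit | 301 ÷ limit |
|---|---|---|
| 50 | 3.26 | 6.02 |
| 100 | 1.63 | 3.01 |
| 150 | 1.09 | 2.01 |
| 200 | 0.82 | 1.51 |
| 250 | 0.65 | 1.20 |
| 300 | 0.54 | 1.00 |

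The whole range exceeds the limit up to about 160 µg/mL, part of it does from there to about 300, and none does above that.

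**4. Cycles 9-24.** No trough is given for 20 mg/kg every 28 days. A one-compartment sketch with an assumed volume of 43 mL/kg gives a 10 mg/kg increment of 10 ÷ 0.043 = 233 µg/mL and a retained fraction per interval r = Cmin ÷ (Cmin + 233) = 0.412 to 0.564. The maintenance trough is 465 × r28 ÷ (1 − r28), where r28 is the fraction left after 28 days.
- If 163-301 are 14-day troughs, r28 = r² = 0.170 to 0.318, giving 95-217 µg/mL.
- If they are weekly troughs, r28 = r⁴ = 0.029 to 0.101, giving about 14-52 µg/mL.

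Section 2.9.5.4 does not say which applies, so nothing firm can be said about maintenance.

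**5. Where a masked CR lands.** VGPR allows protein seen on immunofixation but not electrophoresis, or a 90% fall in serum M-protein with little urine protein. From a baseline of 3 g/dL, a 90% fall leaves 0.3 g/dL, and the drug alone is 0.0163 ÷ 0.3 = 5% to 0.0301 ÷ 0.3 = 10% of that. From 0.5 g/dL it leaves 0.05 g/dL, and the drug is 33% to 60% of that. In both cases drug alone stays under the VGPR ceiling.

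**6. Illustration of size, every input assumed.** True CR 30%, IgG share 50-75%, only IgG patients affected, n = 39. Observed CR = 30% × (1 − IgG share × masked share).

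| IgG CRs masked | Observed CR | Patients lost from CR |
|---|---|---|
| 25% | 24-26% | 1.5-2.2 |
| 50% | 19-23% | 2.9-4.4 |
| 100% | 8-15% | 5.8-8.8 |

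**7. MRD instructions side by side.** Section 11.2.6 limits MRD to patients in CR. Appendix C lists a post-baseline marrow for the sequencing laboratory only at confirmation of CR. The requisition steps in Section 9.2 assign the MRD test to the confirmation-of-response time point. The opening of Section 9, however, also plans samples for that laboratory at Cycle 9 Day 1. These passages do not agree.

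**The case against.** The strongest reply is that the documents never show this antibody to be visible on immunofixation. At an assumed limit of 250 µg/mL, most of the cycle 1-8 trough range and all of the modelled maintenance range lie below it, and maintenance is 16 of the 24 cycles. Readers may already discount a band that does not match the patient's isotype. An IgG patient whose light chain differs from the drug's is distinguishable in any case, and the drug's light-chain type is not given. Section 11.2.4 accepts assessments at any time before new therapy, and Section 5.6 requires immunofixation in follow-up, so some CRs can be scored after the drug has cleared. The EBMT result is collected anyway.

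All of this bears on size, and it stands to that extent. It does not remove the missing rule or the conflict between the two CR definitions. Recovery in follow-up is partial: CR also needs two consecutive assessments and the marrow item, marrow after the end-of-treatment sample is only recommended unless progression is suspected, and no text says a late negative gel reclassifies an earlier response.

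A reader might infer more than the documents support:
- **That a drug band would be read as relapse from CR.** The EBMT item says "Reappearance of serum or urinary paraprotein on immunofixation or routine electrophoresis" and requires confirmation; a band present since early treatment does not reappear.
- **That levels reach 698 µg/mL here.** That figure is from Study 1702, on a different schedule with bortezomib.
- **That a reported stringent-CR rate is biased.** Section 13.1.2 does not list that rate.

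**Conclusion.** The gap is real and rests on the text alone: the main CR definition does not except the study drug, while the protocol's own secondary definition is worded so that it can. Applied as written, the main CR proportion can be under-counted, and MRD with it wherever the test depends on CR.

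The size is unknown. It turns on the immunofixation limit, the drug's light-chain type, the isotype mix and how sites read a non-matching band, none of which the documents give. The illustrated loss of about 3-4 of 39 patients, when half of IgG CRs are masked, is a scenario and not an estimate. It would be too strong to say that CR is under-counted, that only IgG patients are exposed (a literal reading touches every isotype), or that the affected patients lose their MRD result, given the Cycle 9 Day 1 samples in Section 9.

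The effect is confined to secondary results. A masked CR would usually be VGPR, which still counts as an objective response, and the 24-of-39 rule does not use CR. Patients followed only by free light chains have a separate CR rule in Section 11.2.5 and are outside this point.

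**What to change.** 1. In Section 11.2.4, replace the requirement for a negative gel with the EBMT concept: the patient's original monoclonal protein is no longer visible on serum and urine immunofixation. Judge this against the recorded baseline isotype and light chain, and migration position where available. A band that does not match baseline does not exclude CR.
2. Where an IgG patient's band cannot be told from drug, score CR only on two consecutive negative immunofixations with the other CR items met. The off-treatment tests already required by Section 5.6 may count. This keeps the existing two-assessment rule.
3. Report CR by baseline isotype, IgG against non-IgG.
4. Reconcile the opening of Section 9 with Sections 9.2 and 11.2.6 and Appendix C, so that MRD testing does not depend on an uncorrected immunofixation result.

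The cost is wording and one extra table; sample size and decision rule do not change. A few more patients may qualify for a CR marrow and MRD test. The documents do not say that baseline gels are kept, and Section 11.2.9 plans no central response review, so the comparison rests on recorded local results. The main downside is that a few CRs will depend on comparing a band with baseline.

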**But with no evidence of the following CRAB\* criteria or other Myeloma defining events (MDE):**

- Increased calcium levels: Corrected serum **calcium**  $>0.25$  mmol/L ( $>1$  mg/dL) above the upper limit of normal or  $>2.75$  mmol/L ( $>11$  mg/dL)
- **Renal** insufficiency (attributable to myeloma)
- **Anemia** (Hgb  $2$  g/dL below the lower limit of normal or  $<10$  g/dL)
- **Bone** lesions (lytic lesions or generalized osteoporosis with compression fractures)
- Other (symptomatic hyperviscosity, amyloidosis, recurrent bacterial infections ( $>2$  episodes in 12 months).

\*Participants with CRAB criteria that are attributable to conditions other than the disease under study may be eligible

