## 3. PARTICIPANT SELECTION

### 3.1 Eligibility Criteria

3.1.1 Age  $\geq$  18 years.

3.1.2 Must meet criteria of high risk smoldering MM as described with one of the below criteria:

- Bone marrow clonal plasma cells  $\geq$ 10% and any one or more of the following:
  - Serum M protein  $\geq$ 3.0 gm/dL
  - IgA SMM
  - Immunoparesis with reduction of two uninvolved immunoglobulin isotypes
  - Serum involved/uninvolved free light chain ratio  $\geq$ 8 (but less than 100)
    - *Free Light Chain Smoldering Myeloma patients as defined in section 2.4 are not excluded*
  - Progressive increase in M protein level (Evolving type of SMM)†
  - Bone marrow clonal plasma cells 50-60%
  - Abnormal plasma cell immunophenotype ( $\geq$ 95% of bone marrow plasma cells are clonal) and reduction of one or more uninvolved

CONFIDENTIAL

This document is confidential. Do not disclose or use except as authorized.

immunoglobulin isotypes

*\* All patients should have four or six color flow cytometry performed on the baseline bone marrow sample, as feasible. Patients evaluated for eligibility by Spanish Criteria must have their result confirmed by four color flow cytometry. If four or six color flow cytometry is not available at the site, the baseline bone marrow must be sent to Dana-Farber Cancer Institute to confirm eligibility prior to enrollment.*

- t (4;14) or del 17p or 1q gain
- Increased circulating plasma cells
- MRI with diffuse abnormalities or 1 focal lesion ( $\geq 5\text{mm}$ )
- PET-CT with one focal lesion ( $\geq 5\text{mm}$ ) with increased uptake without underlying osteolytic bone destruction

*† Increase in serum monoclonal protein by  $\geq 10\%$  on two successive evaluations within a 6 month period*

3.1.3 No evidence of CRAB criteria\* or new criteria of active MM which including the following:

- Increased calcium levels: Corrected serum calcium  $>0.25\text{ mmol/L}$  ( $>1\text{mg/dL}$ ) above the upper limit of normal or  $>2.75\text{ mmol/L}$  ( $>11\text{mg/dL}$ );
- Renal insufficiency (attributable to myeloma);
- Anemia (Hgb 2g/dL below the lower limit of normal or  $<10\text{g/dL}$ );
- Bone lesions (lytic lesions or generalized osteoporosis with compression fractures)
- No evidence of the following new criteria for active MM including the following: Bone marrow plasma cells  $>60\%$ , Serum involved/uninvolved FLC ratio  $\geq 100$ , and MRI with more than one focal lesion

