Minimal response (MR)	
MR included participants in whom some, but not all, criteria for PR were fulfilled, providing the remaining criteria satisfied the requirements for MR. Required all of the following:
 
≥25% to ≤ 49% reduction in the level of serum monoclonal protein for at least two determinations six weeks apart.
 
If present, a 50 to 89% reduction in 24-hour light chain excretion, which still exceeds 200 mg/24 h, for at least two determinations six weeks apart.
 
25-49% reduction in the size of plasmacytomas (by clinical or radiographic examination) for at least six weeks.
 
No increase in size or number of lytic bone lesions (development of compression fracture does not exclude response).c

No change (NC)	Not meeting the criteria for MR or PD.

CONFIDENTIAL

This document is confidential. Do not disclose or use except as authorized.

Response	Criteria for Response a
Progressive disease (PD) (for participants not in CR)	
Requires one or more of the following:
 
>25% increased in the level of serum monoclonal paraprotein, which must also be an absolute increase of at least 5 g/L and confirmed on a repeat investigation.
 
>25% increased in 24-hour urinary light chain excretion, which must also be an absolute increase of at least 200 mg/24 h and confirmed on a repeat investigation.
 
>25% increased in plasma cells in a bone marrow aspirate or on trephine biopsy, which must also be an absolute increase of at least 10%.
 
Definite increase in the size of existing lytic bone lesions or soft tissue plasmacytomas.
 
Development of new bone lesions or soft tissue plasmacytomas (not including compression fracture).
 
Development of hypercalcemia (corrected serum calcium >11.5 mg/dL or 2.8 mmol/L not attributable to any other cause).

CONFIDENTIAL

This document is confidential. Do not disclose or use except as authorized.

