#### 11.2.8 Progression-Free Survival

Progression-Free Survival (PFS): the primary endpoint in this study. PFS is defined as the time from randomization to the disease progression or death from any cause. Patients who have not

CONFIDENTIAL

This document is confidential. Do not disclose or use except as authorized.

progressed or died are censored at the date last known progression-free.

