### **13. STATISTICAL CONSIDERATIONS**

#### **13.1 Study Design/Endpoints**

The primary endpoint of this phase II study is to determine the proportion of high risk

CONFIDENTIAL

This document is confidential. Do not disclose or use except as authorized.

smoldering multiple myeloma (SMM) patients who are progressive free at 2 years after receiving treatment (Elotuzumab + lenalidomide+ Dexamethasone). The secondary objectives include toxicities, objective response rate, time to progression, duration of response, and overall survival. In addition, we will examine the molecular evolution of the tumor cells, the role of circulating tumor cells and immune cells, and the role of NK cells and other immune cells present in the bone marrow in the progression of smoldering MM.

The proportion of patients who achieve progression free at 2 years will be compared to the rate published for the high risk SMM. By the Mayo Clinic model for risk factors, the median time to progression for patients with high risk SMM was only 1.9 years. Therefore, we assume that for this study, a 2-years progression-free rate of 50% will not be considered promising and a true progression free rate of 70% or higher will be considered promising. A single-stage design will be employed with 39 eligible patients entered. If 24 or more of the 39 eligible patients are progression free at 2 years (observed rate of 62%), we will conclude that this treatment warrants further study. The probability of concluding that the treatment is effective if the true rate is 50% is 0.10 and is >0.9 if the true rate is 70%. Assuming an ineligibility rate of 5%, we will accrue 41 patients/per Arm to the trial in order to have 39 eligible patients. A total of 55 patients will be enrolled.

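### The mg/dL and mmol/L calcium cut-offs in the progression definitions do not agree, and one limb of Section 11.1 is in the wrong unit by a factor of ten

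*Combined protocol and SAP*

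**What the plan says.** Four places set a corrected-calcium limit.

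- **Sections 2.4 and 3.1.3 (eligibility).** Under "Increased calcium levels: Corrected serum" calcium, Section 2.4 rules out a value more than 0.25 mmol/L (1 mg/dL) above ULN, or above 2.75 mmol/L (11 mg/dL). Section 3.1.3 repeats these limits.
- **Section 11.1 (symptomatic disease, called the final endpoint).** The increment is 0.25 "mmol/dL above the upper limit of normal or" an absolute value above .275 mmol/dL. No mg/dL equivalents are given.
- **Section 11.2.4 (IMWG PD).** "development of hypercalcemia (corrected serum calcium" at least 11.5 mg/dL or 2.65 mmol/L), with the condition "that can be attributed solely to the plasma cell proliferative disorder".
- **Section 11.2.6.2 (modified EBMT).** Above "11.5 mg/dL or 2.8 mmol/L not attributable to any other cause". Section 11.1 makes the EBMT criteria a secondary measure.

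Progression feeds the primary analysis. Section 11.2.8 states that "PFS is defined as the time from randomization to the disease progression or death from any cause". Section 13.1 bases its conclusion on at least 24 of 39 eligible patients being progression free at 2 years. Section 13.1.1 estimates the 2-year rate by Kaplan-Meier in all patients who received one dose.

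**The concern.** The two figures in Section 11.2.4 read as one cut-off in two units, but they are different cut-offs. Two sites with the same patient and the same calcium could then reach different answers because their laboratories report in different units. If the word joining the figures is instead taken literally, so that either suffices, the lower one always decides and the 11.5 mg/dL figure has no function.

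The threshold is applied often: Section 10 puts calcium and albumin in the chemistry panel on Day 1 of every cycle. Progression ends protocol therapy (Section 5.5), and central review of response is not planned (Section 11.2.9), so nothing in the plan would bring divergent site readings into line.

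Section 11.1 adds a second difficulty. One of its two calcium limbs is in the wrong unit, and with no mg/dL figures beside it a reader of that section alone cannot see the slip.

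**Working it through.** **Conversion factor.** Section 3.1.3 gives it twice: 11 / 2.75 = 4.0 and 1 / 0.25 = 4.0 mg/dL per mmol/L. The factor from the atomic weight of calcium, 4.008, serves as a check. Also, 1 mmol/dL = 10 mmol/L.

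**Section 11.2.4.** The stated pair, 11.5 mg/dL = 2.65 mmol/L, does not reproduce.
- 11.5 / 4.0 = 2.875 mmol/L (2.869 with 4.008).
- 2.65 × 4.0 = 10.6 mg/dL (10.62 with 4.008).
- Gap: 2.875 − 2.65 = 0.225 mmol/L, or 11.5 − 10.6 = 0.9 mg/dL. This is too large for rounding.

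**Overlap with eligibility.** The highest eligible value is min(2.75, ULN + 0.25) mmol/L, and the overlap runs from 2.65 up to that value. ULN is an assumption, since the documents do not give it.

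| Assumed ULN (mmol/L) | Highest eligible value | Eligible and at the 2.65 PD number |
|---|---|---|
| below 2.40 | below 2.65 | none |
| 2.40 | 2.65 | the single value 2.65 |
| 2.45 | 2.70 | 2.65 to 2.70 |
| 2.50 or more | 2.75 | 2.65 to 2.75 (10.6 to 11.0 mg/dL) |

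Against the 11.5 mg/dL figure there is no overlap, because 11.5 exceeds the eligibility limit of 11 mg/dL.

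**Section 11.1.**
- Increment: 0.25 mmol/dL × 10 = 2.5 mmol/L; 2.5 × 4.0 = 10 mg/dL above ULN. Section 3.1.3 has 0.25 mmol/L (1 mg/dL), so the printed increment is ten times larger and practically unreachable.
- Absolute value: .275 mmol/dL × 10 = 2.75 mmol/L = 11 mg/dL, which matches Section 3.1.3.
- Either limb suffices, so the slip changes a classification only if ULN + 0.25 is below 2.75, that is, if ULN is below 2.50 mmol/L. Values above ULN + 0.25 and up to 2.75 mmol/L are then missed.

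**Section 11.2.6.2.** 2.8 × 4.0 = 11.2 mg/dL, against the 11.5 printed beside it. The gap is 2.875 − 2.8 = 0.075 mmol/L (about 0.07 with 4.008). The same 11.5 mg/dL therefore has two different mmol/L partners in the protocol, 2.65 and 2.8.

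**Weight of one reclassified patient.** 1 / 39 = 2.6 points on the Section 13.1 count. With the 55 patients of Section 13.2 in the Kaplan-Meier analysis, 1 / 55 = 1.8 points before censoring.

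**Design rule.** For a binomial with n = 39, the probability of 24 or more is 0.0998 at a true rate of 50% and 0.906 at 70%. These agree with the stated 0.10 and above 0.9, so the sample size is not in question.

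**The case against.** The strongest reply is that little follows in practice. Several inferences a reader might draw go further than the documents allow.

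- **That an eligible patient can already have PD.** Section 11.2.4 asks for hypercalcemia that develops and is attributable only to the plasma cell disorder. A stable baseline of 2.70 mmol/L meets the number but arguably not the full definition. The overlap also depends on an unstated ULN. This objection stands: what can be shown is that an eligible value may sit at or above one PD number. Because no rise from baseline is quantified, the wording does not fully close the gap.
- **That the tenfold slip causes the overlap or disables Section 11.1.** It does neither. It makes one limb harder to meet, and the .275 mmol/dL limb still operates.
- **That the EBMT pair affects the primary endpoint.** It belongs to a secondary measure, and its mismatch is small.
- **That all sections must share one calcium threshold.** A limit for symptomatic disease and a limit in a response scale may legitimately differ. A difference between Sections 11.1 and 11.2.4 is not in itself an error, and merging them would change the definition of PD.

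It can also be said that response categories need two consecutive assessments. A repeat may filter out a transient value, but it does not tell the site which of two unequal cut-offs to apply. The unit mismatch in Section 11.2.4 and the unit slip in Section 11.1 remain.

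**Conclusion.** The point holds as a unit-consistency error and is minor. In Section 11.2.4 the two cut-offs differ by about 0.22 mmol/L (0.9 mg/dL), so corrected calcium between 10.6 and 11.5 mg/dL is classified differently by unit. This follows from the protocol's own conversion and needs no outside figure. The overlap with eligibility is conditional on local ULN, as tabulated, and on the onset and attribution conditions. The Section 11.1 slip matters only below a ULN of 2.50 mmol/L.

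The number of patients affected cannot be computed from the documents. It is my judgement, not a calculation, that few progressions will turn on calcium alone. The documents do not support a claim that the 2-year rate or the power is materially distorted.

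One uncertainty goes beyond units. Section 11.1 names symptomatic disease as the final endpoint, while Sections 11.2.8 and 13.1.1 count progression without saying which calcium definition applies. A value of 11.2 mg/dL exceeds the 11 mg/dL equivalent in Section 11.1 but not the 11.5 mg/dL figure in Section 11.2.4.

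**What to change.** 1. In Section 11.2.4, make the mg/dL and mmol/L values equivalent. Do the same within the EBMT table in Section 11.2.6.2, including its relapse row.
2. In Section 11.1, express both limbs in mmol/L, matching Section 3.1.3: 0.25 mmol/L above ULN and 2.75 mmol/L. Changing the unit alone is not enough, because .275 must become 2.75 at the same time. Adding the mg/dL equivalents would make any future slip visible.
3. Have the sponsor reconcile Sections 3.1.3, 11.1, 11.2.4 and 11.2.6.2 and state which calcium definition counts as progression for the primary endpoint. Which threshold governs is the sponsor's decision; this review does not propose one.

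Item 2 is a wording correction. Item 1 is also one, once the sponsor has said which figure in each pair is intended. Item 3 needs a short sponsor decision. If patients have already been classified on calcium, their values should be checked against the reconciled definition. None of this affects the sample size or the decision rule.
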